
Secondary Endpoints
	
 1. Adverse events: rate, severity, seriousness, relatedness to stent or endoscopic or surgical procedure, impact on time of surgery, length of hospitalization and ICU stay 2. Time to surgery 3. Curative Intent Surgery details pertaining to intraoperative assessment of resectability, surgical resection and reconstruction techniques 4. Intraoperative blood loss and blood transfusions, duration of surgery 5. Biliary obstructive symptoms assessment (Week 2, surgery/transition to palliation, 30 day post-operative follow up and 120 day follow up) 6. Improvement of LFT levels as relative to baseline (Week 2, surgery/transition to palliation, 30 day post-operative follow up and 120 day follow up) 7. Stent placement success: ability to deploy the stent in satisfactory position across the stricture (Group 2) 8. Stent removal success: successful SEMS removal, either en bloc at time of surgery or endoscopically prior to surgery without stent removal related SAEs 9. Number, type, reason and timing of biliary re-interventions 10. Number and duration of hospital and ICU admissions

Follow-up Schedule and Assessments
	
 • Screening: Count all consecutive patients seen at investigational site presenting with biliary obstructive symptoms and suspicion of pancreatic cancer, distal common bile duct cholangiocarcinoma or peri-ampullary cancer. Of those, a subset will be invited to participate in trial: Informed Consent (enrollment) and Eligibility Criteria Assessment • Baseline Visit (Day 0): Demographics, Medical History, Tumor Diagnosis, Staging and Characteristics, Assessment of Biliary Obstructive Symptoms, Laboratory Tests, Randomization • Stent Placement Procedure Visit (Group 2 only, Day 0): Stent Details, Procedure Details, Adverse Events (AEs) • Pre-Operative Visit (Week 2): Assessment of Biliary Obstructive Symptoms, Laboratory Tests, AEs 
Group 1 (No Pre-Operative Biliary Drainage): Patients will undergo resection per institutional standard of practice. Time to surgery is not to exceed 4 weeks unless there is a need to delay

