	
planned surgery due to a complication, biliary obstructive symptoms, decline in patient physiologic status, or other factors that preclude surgery.
 
Group 2 (Pre-Operative Biliary Drainage with a SEMS): Patients will undergo resection after resolution of jaundice is achieved (defined as Bilirubin below 100µmol per liter), or at 4 weeks, whichever comes first.
 
 • Biliary Reintervention Visit (as needed): Timing, Reason for Biliary Reintervention, Type of Biliary Reintervention, AEs Group 1 patients who fail their treatment algorithm by requiring biliary drainage prior to surgery will receive a study SEMS. Group 2 patients who require re-stenting or placement of a stent for a new stricture, will receive a study SEMS. • Curative Intent Surgery: Assessment of Biliary Obstructive Symptoms, Laboratory Tests, Operative Details, Stent Removal, Blood Loss, Intra- and Post-Operative Transfusion, Post-Operative Course, Specimen Pathology, AEs • Transition to Palliative Management Visit (as needed): Assessment of Biliary Obstructive Symptoms, Laboratory Tests, AEs • Post-Operative Follow up Visit (30 days Post-Surgery, if applicable): Assessment of Biliary Obstructive Symptoms, Laboratory Tests, AEs • Long Term Follow-up Visit (120 days--150 days post randomization): Assessment of Biliary Obstructive Symptoms, Laboratory Tests, AEs 
Patients who undergo surgery as planned will be evaluated at 30 days post-surgery and will be followed up to 120 days after randomization.
 
Patients with delay in planned surgery may require follow up longer than 120 days to allow for a 30 day post-surgery follow up visit but follow up is not to exceed 150 days post-randomization.
 
Patients with a delay in planned surgery whose rescheduled surgery is unable to occur within 120 days will be followed up to 120 days after randomization.
 
Patients who do not undergo surgery as planned due to conversion to palliative management or patient choice will be followed up to 120 days after randomization. If patient's course of treatment requires placement of a biliary stent, stenting will be done per

--	---

	
standard of care at each institution. If a metal stent is required, a study WallFlex Biliary FC stent will be placed.

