5 ADDITIONAL DATA ANALYSES

5.1 Secondary Endpoints

1. Adverse events: rate, severity, seriousness, relatedness to stent or endoscopic or surgical procedure, impact on time of surgery, length of hospitalization and ICU stay
2. Time to surgery
3. Curative Intent Surgery details pertaining to intraoperative assessment of resectability, surgical resection and reconstruction techniques
4. Intraoperative blood loss and blood transfusions, duration of surgery
5. Biliary obstructive symptoms assessment (Week 2, surgery/transition to palliation, 30 day post-operative follow up and 120 day follow up)
6. Improvement of LFT levels as relative to baseline (Week 2, surgery/transition to palliation, 30 day post-operative follow up and 120 day follow up)
7. Stent placement success: ability to deploy the stent in satisfactory position across the stricture (Group 2)
8. Stent removal success: successful SEMS removal, either *en bloc* at time of surgery or endoscopically prior to surgery without stent removal related SAEs
9. Number, type, reason and timing of biliary re-interventions and time to first re-intervention.
10. Number and duration of hospital and ICU admissions

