5.8 Analysis of Impact of Adverse Events on Endpoints

For an analysis on the effect of the adverse events impact on time of surgery, length of hospitalization, and ICU stay, subjects with and without AEs will be analyzed to determine if any differences occur. Appropriate testing will be done to determine this, i.e. a 2x2 ANOVA analysis with a treatment interaction.

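### SAP 5.8 sets no onset limit on AEs when it asks whether they affected the time of surgery, so read as written it shrinks any true delay

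*SAP*

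**What the plan says.** Secondary endpoint 1 (SAP 5.1) includes, for adverse events, "impact on time of surgery, length of hospitalization and ICU stay". Section 5.8 gives the analysis: "subjects with and without AEs will be analyzed to determine if any differences occur", and the test it names is "a 2x2 ANOVA analysis with a treatment interaction". One AE grouping serves all three outcomes, and nothing in 5.8 or elsewhere restricts when the AE must have begun.

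AE collection runs well past surgery. The schedule in section 1 lists "Post-Operative Follow up Visit (30 days Post-Surgery, if applicable): Assessment of Biliary Obstructive Symptoms, Laboratory Tests, AEs" and "Long Term Follow-up Visit (120 days--150 days post randomization): Assessment of Biliary Obstructive Symptoms, Laboratory Tests, AEs". The complication definitions in 7.3 include a surgery-related group (anastomotic leakage, delayed gastric emptying, wound infection) that can only follow the operation.

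The SAP treats delay as a live question. For Group 1 it sets a four-week limit on the wait, which may be exceeded by postponing "planned surgery due to a complication, biliary obstructive symptoms, decline in patient physiologic status, or other factors that preclude surgery". It also expects that some patients will never be operated on, "due to conversion to palliative management or patient choice will be followed up to 120 days after randomization".

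**The concern.** An event that starts after the operation cannot have changed its date. If such events define the AE group, that group mixes patients whose surgery could have been delayed by an AE with patients for whom this is impossible, and the contrast is pulled towards zero.

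A second weakness is separate. Whether a patient has had an AE by the end of follow-up depends partly on how long the patient was at risk in each period. A longer wait gives more time for a pre-operative AE, so a fixed yes/no factor can be associated with the wait even when AEs have no effect on it.

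At stake is the answer to one component of a secondary endpoint: a real delay caused by complications could be understated or missed. The primary comparison of serious adverse events does not use this analysis.

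**Working it through.** **The plan's own figure.** Section 5.8 states none. The only reproducible figure is the sample size, used here to set n. With 37.2% in both arms, a margin of 15%, one-sided 5% and 80% power, the asymptotic formula gives 129 per arm. The exact power of the Farrington-Manning test at 132 per arm is 80.3%, and 132/0.90 = 146.7, so 147. The stated 132 and 147 stand.

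**Dilution.** Let p be the share of patients with an AE before surgery, q the share of the others with an AE only after surgery, and D the true delay. The AE versus no-AE contrast is

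D × p / (p + (1 − p)q) = D × P(pre-operative AE)/P(any AE).

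The SAP gives neither p nor q, so these are assumptions:

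- p = 0.10, q = 0.5: 0.10/0.55 = 18% of the delay remains.
- p = 0.20, q = 0.5: 0.20/0.60 = 33%, so 7 days becomes 2.3.
- p = 0.40, q = 0.2: 0.40/0.52 = 77%.

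A partial anchor is the SAP's 37.2% complication rate, used as if it were P(any AE). All AEs together are probably more frequent. With pre-operative AEs in 5, 10 or 18% of patients, 7 days becomes 7 × 5/37.2 = 0.9, 7 × 10/37.2 = 1.9 or 7 × 18/37.2 = 3.4 days.

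**Simulation of the 2x2 ANOVA.** Assumptions: 132 per arm, two-sided 5%, waits uniform on 5 to 28 days in both arms, constant pre-operative AE hazard, a 7-day delay after a pre-operative AE, and 10% never operated on and excluded. Apparent delay, with the rejection rate for the AE main effect:

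| Post-operative AE rate | 0.3%/day | 0.6%/day | 1.2%/day |
|---|---|---|---|
| 30% | 1.4 d (32%) | 2.5 d (74%) | 4.2 d (99%) |
| 50% | 0.9 d (17%) | 1.7 d (44%) | 3.0 d (87%) |
| 70% | 0.7 d (9%) | 1.3 d (21%) | 2.3 d (53%) |

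Two other wait patterns, differing between arms, gave 0.7 to 4.1 and 0.5 to 3.0 days. Hand check at the mean wait of 16.5 days: a hazard of 1.2%/day gives p = 1 − exp(−0.198) = 0.18. With q = 0.3, dilution alone leaves 7 × 0.18/(0.18 + 0.82 × 0.3) = 3.0 days. The simulated 4.2 is larger because the time-at-risk error adds to it.

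**No true delay.** Across the three wait patterns the AE main effect is rejected in 5 to 33% of trials. It is near nominal (about 5 to 7%) at the lowest hazard, and 4.5 to 5.6% when hazards before and after surgery are equal. A second set of assumptions (mean waits 21 and 28 days, SD 8) shows the sign can change. Pre- and post-operative hazards of 0.02 and 0.005 per day give +1.6 days (34% rejected), 0.01 and 0.01 give 0.0 days (5%), and 0.002 and 0.02 give −1.3 days (14%).

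**The simple repair.** Keeping a yes/no factor but restricting it to pre-operative AEs removes the dilution and leaves the time-at-risk bias undiluted. With no true delay it rejects in 13 to 81% of trials. In the second set, a hazard of 0.008 per day gives +2.9 days (62%).

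**Time-dependent Cox model.** With no true delay, error was about 3 to 6% under every censoring rule tried. Detection of a 7-day delay depends on when non-operated patients are censored: 85 to 100% with censoring up to 14 days after the planned date, and 42 to 96% with these patients held to day 120. A smaller run with day-120 censoring (120 trials per cell) gave 31 to 99%. At its lowest hazard that is no better than the ANOVA's 32% in the table. Adding the arm-by-AE term lowered detection to about 87% at 0.3%/day.

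**The case against.** The strongest reply is that 5.8 is silent rather than wrong. It does not say in words that post-operative AEs count towards time of surgery. Its single grouping also serves hospital and ICU stay, for which post-operative AEs belong, and a sensible analyst might count only earlier AEs for surgery timing. That stands as a description of the text: the inclusion follows from unrestricted wording and the length of AE collection, not from an explicit instruction. It does not remove the point, because the restriction that analyst would reach for is itself biased.

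A reader might infer that the analysis mainly contrasts patients with and without post-operative AEs. The documents do not support that. Under the simulated rates, 57 to 94% of the AE group has only a post-operative AE, but with q = 0.2 and p = 0.20, 0.30 or 0.40 the share is 44, 32 or 23%. The SAP gives no rates that would decide between these.

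A reader might also infer that 5.8 will generate false delays. It may, but the bias can equally be absent or negative, and in the simulations with a fixed post-operative risk, post-operative AEs weaken it.

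It is also fair that reporting time to surgery among operated patients only is not an error. It simply leaves open whether AEs prevented surgery. 'Time of surgery' could mean duration of the operation, but an AE starting afterwards cannot affect that either. Finally, this is one clause under additional analyses with no decision attached, and 5.10 allows documented changes before analysis.

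**Conclusion.** The point holds in a limited form. As written, 5.8 lets AEs that begin after surgery define the AE group for time of surgery, and a true delay shrinks to P(pre-operative AE)/P(any AE). The direction of the dilution is certain whenever some patients have only post-operative AEs. Its size is not: 7 days appears as about 0.5 to 4.2 days under assumed waits, hazards and post-operative rates, none of which the SAP supplies. The time-at-risk bias is real but conditional on those rates. The sample size and the primary non-inferiority conclusion are untouched. The SAP should be changed here because it names a specific analysis for a listed secondary endpoint and a better one uses dates the trial already holds.

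**What to change.** In 5.8, for time to surgery only:

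- Count AEs with onset after randomisation and before surgery.
- Fit a Cox model from randomisation, stratified by arm, with AE as a time-dependent covariate (0 before onset, 1 from onset). Keep the arm-by-AE interaction as a secondary term. Do not use a yes/no pre-operative factor.
- Censor non-operated patients when they stop being surgical candidates (decision for palliation, refusal, or death), not at day 120, because late censoring costs power.
- Tabulate non-operation by pre-operative AE status and arm, since the model does not show whether AEs prevented surgery.
- State how AEs with imputed onset dates are classed. Section 7.3 sets a wholly missing onset to the procedure date and moves partial dates to the start of the month or year, which could turn a post-operative AE into a pre-operative one.
- Describe the hospital and ICU stay comparisons as associations.

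The cost is SAP wording and modest programming. AE and surgery dates already feed the rules in 7.3, and 5.5 already names proportional hazards regression for time-to-event outcomes. The result becomes a hazard ratio instead of a difference in days, though median days by group can be shown beside it. Power will be limited if pre-operative AEs are rare, and lower again if the interaction is included.

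### The ANOVA in SAP 5.8 has no place for patients who are never operated, so the impact of adverse events on time of surgery is understated if they cancel operations

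*SAP*

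**What the plan says.** Section 5.8 compares subjects with and without AEs on three outcomes, introduced as "For an analysis on the effect of the adverse events impact on time of surgery, length of hospitalization, and ICU stay". The method follows: "Appropriate testing will be done to determine this, i.e. a 2x2 ANOVA analysis with a treatment interaction". This serves secondary endpoint 1 in section 5.1, which includes the "impact on time of surgery, length of hospitalization and ICU stay".

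The follow-up schedule in section 1 describes patients who will have no surgery date:

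- Those who do not have the planned operation "due to conversion to palliative management or patient choice will be followed up to 120 days after randomization".
- Those with a delayed operation "whose rescheduled surgery is unable to occur within 120 days will be followed up to 120 days after randomization".
- The schedule also holds a visit for the first of these routes: "Transition to Palliative Management Visit (as needed): Assessment of Biliary Obstructive Symptoms, Laboratory Tests, AEs".

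The Group 1 paragraph of the same schedule names a complication and a decline in physiologic status among the reasons for which planned surgery may be put back. No section says how a patient without a surgery date enters the analysis in 5.8.

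**The concern.** The most serious effect an AE can have on surgery timing is that the operation does not take place. Under an ANOVA that patient contributes nothing, while a patient delayed by a week contributes seven days. The comparison is then made in a subset selected by the consequence it is meant to measure. The treatment-by-AE interaction is estimated in the same subset. A reader could conclude that AEs barely affect surgery when their main effect was to lose operations.

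**Working it through.** **Plan's own figure.** Section 5.8 states none. The only computed design figure in the SAP is the primary sample size. It reproduces (129 per arm by normal approximation; exact Farrington-Manning power 0.804 at 132 per arm; 132/0.9 = 146.7, rounded up to 147) and has no bearing on this point.

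**Step 1: who is in the ANOVA.** It needs a number of days for each patient. A patient converted to palliation, declining surgery, or not operated by day 120 has no such number, and none is assigned. The analysis is therefore confined to operated patients. The SAP does not say this in words; it follows from the method.

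**Step 2: is the loss related to AEs?** The schedule allows a complication to delay surgery and recognises that a delayed operation may not occur within 120 days. Together these make it plausible that a missing surgery date follows from an AE. They do not establish how often.

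**Step 3: size, on assumed rates.** All inputs are assumptions except day 120, which is the SAP's follow-up limit for unoperated patients.

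- Mean time to surgery without an AE: 14 days.
- Never operated: 5% without an AE; a proportion c, from 10% to 30%, with an AE.
- Yardstick: restricted mean time to surgery over 120 days in all patients, counting a never-operated patient as 120 days.

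*(a) AEs cancel but do not delay.* Operated patients average 14 days in both groups, so the ANOVA difference is 0. The all-patient difference is

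[120c + 14(1 − c)] − [120 × 0.05 + 14 × 0.95] = 106 × (c − 0.05).

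- c = 0.10: 106 × 0.05 = 5.3 days
- c = 0.20: 106 × 0.15 = 15.9 days
- c = 0.30: 106 × 0.25 = 26.5 days

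*(b) AEs add a mean delay of 14 days, and the longest waits become cancellations* (simulated).

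*(c) The same delay, with cancellation independent of its length* (simulated).

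| Never operated with AE (5% without) | (b) ANOVA | (b) all patients | (c) ANOVA | (c) all patients |
|---|---|---|---|---|
| 5% | 11.8 | 11.1 | 14.0 | 13.3 |
| 10% | 10.3 | 14.6 | 14.0 | 17.8 |
| 20% | 8.2 | 22.5 | 14.0 | 27.2 |
| 30% | 6.4 | 31.0 | 14.0 | 36.4 |

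Entries are differences in days, AE minus no AE.

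**Step 4: reading.** With equal cancellation (first row, and c = 0.05 in the formula for (a)) the two measures agree within 0.7 days. With more cancellation after an AE, the ANOVA difference is smaller than the all-patient difference in every case. In (b) it falls from 10.3 to 6.4 days while the all-patient difference rises from 14.6 to 31.0. If cancellation were less frequent after an AE, the sign of c − 0.05 in (a) shows that the error would run the other way.

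**The case against.** **What stands.** Understatement depends on a difference in cancellation that the SAP does not quantify. The mean difference among operated patients is a legitimate, narrower quantity: in (c) the ANOVA recovers the full 14-day delay. The analysis sits under additional analyses, carries no alpha or success criterion, and can still be changed under section 5.10. The opening words of the method sentence suggest some latitude, although what follows names one method.

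**Stronger readings that the document does not support.**

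- *That secondary endpoint 2, "Time to surgery", is itself analysed by ANOVA.* Section 5.8 names ANOVA only for the impact of AEs. Section 5.3 is a general rule for descriptive summaries. The SAP names no test for endpoint 2.
- *That AE impact is certainly understated.* This requires more cancellation after an AE.
- *That the arms must differ because drainage lengthens the wait.* Section 1 gives both arms a four-week planning limit, with exceptions for Group 1, and Group 2 may go earlier once bilirubin falls. The SAP shows no difference in lost operations between arms.
- *That the schedule lists death as a reason for no surgery.* It does not. Death is only defined as a complication in section 7.3, though a patient who dies before surgery plainly has no surgery date.

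**Could time of surgery mean its length?** Secondary endpoint 4 lists that separately ("Intraoperative blood loss and blood transfusions, duration of surgery"), so timing is the natural reading. The term should still be defined.

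**Do other sections cover it?** Proportional hazards regression appears for the poolability check (5.5) and a Cox model for predictors of serious AEs (5.6). Neither is applied here.

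**Conclusion.** The point holds for the time-of-surgery part of section 5.8. The named method cannot use patients who are never operated, the document expects such patients, and it gives no rule for them. The impact of AEs is understated if operations are lost more often after a pre-operative AE, which the schedule makes plausible but does not show. On assumed never-operated rates of 10% to 30% against 5%, with no delay, 0 days is reported where the all-patient 120-day difference is about 5 to 27 days. With equal rates the distortion is negligible. The figures depend on the assumed 14-day mean and on counting unoperated patients as 120 days. The consequence is limited to secondary endpoint 1; the primary endpoint is not touched.

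**What to change.** For the time-to-surgery part of 5.8 only:

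1. Define time of surgery as time from randomization to curative-intent surgery, and analyse it in the ITT cohort.
2. Use a cause-specific proportional hazards model with treatment, AE and their interaction. Count only AEs with onset before surgery (or before a competing event), and enter AE as a time-dependent covariate. A fixed indicator would introduce immortal-time bias, because patients who wait longer have more time to acquire an AE, and it would let post-operative AEs predict a surgery date already past.
3. Treat death and conversion to non-surgical management (palliation or patient choice) as competing events, with administrative censoring at day 120.
4. Report the proportion never operated by arm and by pre-surgery AE status. This is essential: patients leave the risk set at a competing event, so the hazard ratio for surgery alone can miss cancellations. The same model fitted to the competing events would complete the picture.
5. Give the cumulative incidence of surgery by arm as a summary for secondary endpoint 2.

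The cost is SAP wording and standard SAS procedures. The surgery date is listed in section 7.3, and the schedule has a visit for transition to palliation; whether the date of that decision, or of a patient's refusal, is recorded should be confirmed. The small downside is that the result is a hazard ratio and cumulative incidence, not a mean number of days. The mean among operated patients can stay as a labelled description.

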5.9 Baseline Tumor Stage vs. Pathology Tumor Stage

A frequency table will be conducted to look for the differences between the baseline tumor stage and the pathology tumor stage diagnosis. This table will include all stages including a missing category for both time points.

